## Serological study of COVID-19 prevalence in St.Petersburg

### PARTICIPANT QUESTIONNAIRE

ATTENTION! Please select most appropriate answers from your own point of view. If you have any doubt, select approximate answer. To avoid introducing bias into the study results, the clinic staff cannot give explanations. Your answers will not affect the decision about conducting the test and will be used in anonymized form.

**1. Your body weight (may be approximated) is \_\_\_\_\_ (kg)**

**2. Your height (may be approximated) is \_\_\_\_\_ (cm)**

**3. Do you smoke?**

 No	 Yes
Did you smoke before?	At what age did you start smoking? _____
 No  Yes	Usually, do/did you smoke cigarettes?
Go to Question 4	 No  Yes
Please answer when you quit smoking most recently and answer the questions on the right	Go to Question 4
I quit smoking in the year_____.	How many cigarettes per day do/did you usually smoke?
	 Less than half a pack (10 cigarettes) per day
	 Approximately a pack (10-20 cigarettes) per day
	 More than a pack (20 cigarettes)

**4. How often did you drink alcohol (including beer) in the last 30 days?**

 Every day	 4-6 times per week	 2-3 times per week
 Once a week	 2-3 times in the last 30 days	 Once in the last 30 days
 Never		

**5. Have you visited a hospital or a clinic since the beginning of February?**

 No	 Yes
-----------------------------	------------------------------

**6. Have you had any common cold since February?**

 No	 Yes
-----------------------------	------------------------------

**7. For professional or other reasons, do you have to contact with people often?**

 No	 Yes
-----------------------------	------------------------------

**8. Have you used public transport in the last 2 weeks? If yes, how often?**

- ☐ At least once a day per week ☐ Several times per week
- ☐ Once a week or less ☐ Never

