## 3. Study procedures

### 3.1.Study design

This non-interventional observational socioepidemiological population study will be conducted in residents of St. Petersburg, Russia. Selection and invitation of participants will take place during telephonic survey. After giving signed informed consent, each participant will be subjected to a blood test for SARS-CoV-2 antibodies and will answer a questionnaire. The testing will be performed primarily using serological assays for serum IgG approved in the Russian Federation (Abbott Architect IgG and Genetico).

This study involves a telephonic sociological survey during which respondents will be invited to undergo a blood test for SARS-CoV-2 antibodies at the participating investigational sites in different cities and towns of Russia. The participants will undergo such a test, take part in an additional survey for those who plans or have already done such a test, and receive the results. A part of participants will be offered to use a taxi (see Section 5.2). Testing and questionnaire at the clinic will be repeated several times. It is planned to perform up to 10 visits which will include blood sampling, testing, and collection of additional information.

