### **3.3. Data collection**

During the study, the information will be collected from 3 sources:

- 1. Information collected via telephonic surveys (see Appendix 1);
- 2. Information collected during interviews at the clinical sites (see Appendix 2);

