## 5.2. Encouragement design

Even if random sample of potential participants (surveyed persons) is representative, the decision about the participation in the study may bias its results, as it is made (or rejected) by a potential participant. The assumption of ideal participation of all surveyed persons in the testing is unrealistic. The next step would be to assume self-selection based on the observed characteristics of the surveyed. But it is doubtful that during a telephonic interview all observed individual characteristics which may affect the decision about the participation may be identified and quantified. For this reason, the final assessment of the prevalence will be biased. To surpass the issue of non-observable decision about the voluntary participation, the encouragement design will be used in this study.

A randomly selected subgroup of the surveyed will be offered a benefit related to the study participation, free-of-charge taxi to the place of testing. This offer will be made during the interview. Such randomization will permit to assess the proportion of infected in the group of people whose decision to participate in the testing changes depending to this benefit. The prevalence assessed in this manner has higher external validity than the prevalence in the group of people who make the decision without external encouragement.

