(A SINGLE ANSWER) DisableReordering Single choice from 'Q8 list'

1       Yes

2       No

Q9     Single choice from 'Q9 list'

Q8=1

How often have you been outdoors during the last week (7 days)?

(A SINGLE ANSWER)

Q10 Single choice from 'Q10 list'

Q8=1

How much time have you spent out of your home when you went out most recently?

(IF THE ANSWER CONTAINS INTERVAL, REGISTER THE UPPER BORDER.

REGISTER HOURS OR MINUTES — 30 min, 20 min

IF THE ANSWER CONTAINS HOURS AND MINUTES, REGISTER AS IT IS: 1 h 10 min, 2 h 40 min)

999 (DON'T READ) Not sure

Q11 Multiple choice from 'Q11 list'

Q8=1

Which of the following places have you visited during the last week?

(ANY NUMBER OF ANSWERS)

1 Work

2 Metro and other public transport, including taxi

3 A pharmacy

4 A shop or a market

5 A post office, a bank, an ATM, a medical institution

6 I have not been to any of these places

Q12

Have you had any examination for coronavirus?

(DON'T READ ANSWERS)

(A SINGLE ANSWER) DisableReordering,

Blocking

Single choice from 'Q12 list'

1 Yes

2 No

Q121 Single choice from 'Q121 list'

Q12=1

The result of this examination was:

(A SINGLE ANSWER)

1 Positive

2 Negative

3 I don't know

999 (DON'T READ ANSWERS) Not sure

Q13 Single choice from 'Q13 list'

Do you or do you not follow information regarding coronavirus? If you follow, do you do it continuously or once in a while?

(DON'T READ ANSWERS)

(A SINGLE ANSWER)

1 Follow continuously

2 Follow once in a while

999 (DON'T READ ANSWERS) Not sure DisableReordering

Q15 Single choice from 'Q15 list'

Q8=1

Were you wearing a mask when leaving your home during the last week?

(DON'T READ ANSWERS)

(A SINGLE ANSWER)

1 Yes

2 No

Q16 Single choice from 'Q16 list'

Q8=1 and Q15=1

Were you wearing a mask while just outdoors?

(DON'T READ ANSWERS)

(A SINGLE ANSWER)

1 Yes

2 No

Q17

Can you say that now you wash your hands more often than before the epidemics?

(DON'T READ ANSWERS)

(A SINGLE ANSWER) Single choice from 'Q17 list'

1 Yes

2 No

999 (DON'T READ) Not sure

Q19

In your opinion, should the limitations for public have been stricter or not?

(DON'T READ ANSWERS)

(A SINGLE ANSWER) DisableReordering Single choice from 'Q19 list'

1 Yes, they should have been

2 No, they should not have been

999 (DON'T READ) Not sure DisableReordering

Q20 Single choice from 'Q20 list'

Q19=2

In your opinion, should the limitations for public have been less strict or not?

(DON'T READ ANSWERS)

(A SINGLE ANSWER)

1 Yes

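### Minor: Questions 5 and 8 of the clinic questionnaire do not exclude the study's own visits and travel, so the trip to the test can be recorded as exposure

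*Protocol*

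**What the plan says.** Protocol Section 3.3 has the Appendix 2 information collected at the clinical sites. Two of its items matter here:

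- Question 5: "Have you visited a hospital or a clinic since the beginning of February", answered No or Yes.
- Question 8: "Have you used public transport in the last 2 weeks? If yes, how often", with four frequency categories, of which the lowest two are "Once a week or less" and 'Never'.

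Neither item mentions visits or trips made for this study. The instructions at the top of the form rule out help on site: "To avoid introducing bias into the study results, the clinic staff cannot give explanations".

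Section 5.2 adds a randomised offer: "A randomly selected subgroup of the surveyed will be offered a benefit related to the study participation, free-of-charge taxi to the place of testing". Question 8 does not say whether a taxi is public transport. The telephone survey does: option 2 of Q11 in Appendix 1 reads "Metro and other public transport, including taxi".

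On follow-up, Section 3.1 says "Testing and questionnaire at the clinic will be repeated several times", with up to 10 visits four weeks apart, and wants repeat questionnaires to cover the time from the first test onward. Appendix 2 is the only clinic form shown, and its completion line is pre-printed for May or June 2020.

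**The concern.** A participant who fills in Appendix 2 has just made a journey to a clinic. Read literally, that journey and that visit belong in the answers. Someone who otherwise stayed at home but came by metro cannot truthfully tick 'Never' in Question 8. Yet travel to the blood draw cannot have caused the antibody result of that draw. Counting it as exposure moves unexposed people into the exposed group and pulls any association towards the null.

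The taxi offer can change the mode of travel in a random subgroup, so the rate of this error may differ between those offered and not offered a taxi. Which group is affected more depends on whether respondents count the taxi, and the form leaves that open.

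Section 2.2 names mobility as a factor whose relation to infection risk is to be evaluated. 'Never' is a natural reference category for a transport item. Later analysis cannot separate study travel from other travel if the form did not ask for it.

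**Working it through.** **Which study trips can count.** Question 8 looks back 14 days and visits are planned 28 days apart. No earlier study visit falls in the window; only the current outbound trip does. One trip can move 'Never' to the lowest user category and should hardly affect the higher ones.

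**Question 5 at follow-up.** The protocol's attrition table reproduces: 1000 × 0.95^9 = 630.2, stated as 630. Summing the table, visits 2 to 10 give 950 + 902 + 857 + 815 + 774 + 735 + 698 + 663 + 630 = 7024 forms, out of 7024 + 1000 = 8024, or 87.5%. If the same form is used at those visits, each of these respondents has already made one clinic visit after February, namely the first study visit. Every truthful answer is then Yes and the item has no variation there.

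**Dilution in Question 8.** The protocol gives no figure for travel mode, taxi uptake or allocation ratio, so all inputs are assumptions. Collapse the item to any use versus never. Let u be the true share of users, R the true prevalence ratio, and m the share of true non-users recorded as users because of the study trip. The baseline prevalence cancels:

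observed ratio = [uR + (1 − u)m] / [u + (1 − u)m]

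With equal offer groups and the error in one group only, the pooled analysis uses m/2. For R = 2.0:

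| u | m in one group | Ratio in that group | Pooled ratio |
|---|---|---|---|
| 0.5 | 0.10 | 1.05/0.55 = 1.91 | 1.025/0.525 = 1.95 |
| 0.5 | 0.30 | 1.15/0.65 = 1.77 | 1.075/0.575 = 1.87 |
| 0.5 | 0.50 | 1.25/0.75 = 1.67 | 1.125/0.625 = 1.80 |
| 0.3 | 0.10 | 0.67/0.37 = 1.81 | 0.635/0.335 = 1.90 |
| 0.3 | 0.30 | 0.81/0.51 = 1.59 | 0.705/0.405 = 1.74 |
| 0.3 | 0.50 | 0.95/0.65 = 1.46 | 0.775/0.475 = 1.63 |

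The pooled column is the relevant one, because no analysis by offer group is planned for the risk factors.

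**Wider range.** Let the true share of 'Never' run from 30% to 70%, with m from 0.1 to 0.6 without a taxi offer and 0 to 0.1 with it. A true 2.0 then becomes 1.98 to 1.55, and a true 1.5 becomes 1.49 to 1.28.

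**If respondents count the taxi.** Take m = 0 without the offer and 0.6 with it, at u = 0.5. Recorded 'Never' is then 50% against 20%, so the gap lies in the other group. The pooled ratio for a true 2.0 is (1 + 0.15)/(0.5 + 0.15) = 1.77.

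**What does not move.** The sample size formula in Section 5.1 contains only prevalence and margin of error. Telephone items Q8 to Q11 are asked before any study trip.

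**The case against.** The strongest reply is that little depends on these two items, and most of that reply stands.

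- No planned analysis names Question 5 or Question 8. Section 5.3.2 specifies ratios for sociodemographic factors, and clinic contact appears in no objective.
- Mobility is already measured by telephone items Q8 to Q11, including places visited and public transport, before any travel to the clinic.
- The pre-printed May/June date and the Section 3.1 wording on repeat questionnaires suggest that Appendix 2 may be a baseline form only.
- The dilution is small next to sampling error. With 1000 participants, 10% prevalence and 50% users, the expected cases are 66.7 and 33.3 in groups of 500. The standard error of the log ratio is √(0.8667/66.7 + 0.9333/33.3) = 0.20, so a ratio of 2.0 has a 95% interval of about 1.3 to 3.0.
- The instructions invite an approximate answer in case of doubt, so not every respondent will read the item literally.

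A reader might also infer that the randomised taxi offer is compromised as an instrument and that the prevalence estimates are biased. The document does not support this. The imputation and selection corrections in Section 5.3 need characteristics of people who were not tested, and Appendix 2 exists only for those who reached the clinic.

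These points limit the consequence. They do not supply the missing exclusion or the missing definition of taxi, and both can be put right on the form.

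**Conclusion.** The point holds at minor severity. As worded, Question 8 can record the trip to the test as exposure, mainly by moving 'Never' to the next category, and the rate may differ by taxi offer. A mobility association based on that item would be modestly diluted: about 1.95 to 1.80 for a true ratio of 2.0, assuming 50% users, equal offer groups and 10% to 50% of non-users misrecorded in one group.

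Three stronger readings are tempting and go too far.

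- Question 5 is not shown to be Yes for everyone. At the first visit that requires the respondent to count the visit in progress; from Week 4 it requires this form to be reused, which the protocol leaves open.
- The taxi is not shown to remove the error in one group. Travel mode and uptake are unknown, and the direction can reverse.
- Telephone Q11 and Question 8 do not contradict each other. One includes taxi and the other is silent, which is an ambiguity.

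**What to change.** - In Questions 5 and 8 of Appendix 2, add: *not counting visits or travel for this study*.
- State in Question 8 whether a taxi counts, using the same definition as Q11 of the telephone survey.
- If Appendix 2 is used again at later visits, make its look-back match the follow-up period in Section 3.1, which starts at the first test.

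This changes a few words on a form and needs no extra visit, staff or test. The cost is that forms already completed under the present wording will not be fully comparable with later ones.

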**9. Do you or your blood relatives (parents, children, siblings) have hereditary diseases?**

- ☐ I don't know ☐ No ☐ Yes (which) \_\_\_\_\_

**10. If you have any of the following chronic diseases, please, mark all applicable options**

- ☐ Diabetes. If yes, do you receive insulin? ☐ No ☐ Yes
- ☐ Emphysema, chronic bronchitis, other respiratory diseases except asthma.
- ☐ Asthma. If yes, which of the following did you use during the last month (select all applicable options)?
- ☐ Manual inhalers
  - ☐ Oral medications
  - ☐ Oral steroids
  - ☐ Oral nebulizer at home
  - ☐ Other

- ☐ Renal failure
- ☐ Chronic hepatic diseases, for example, hepatitis or cirrhosis
- ☐ Cardiovascular diseases
- ☐ Hematological disorders, for example, chronic anemia
- ☐ Other chronic diseases or disorders not mentioned above. If yes, describe them:

What treatment do you receive? \_\_\_\_\_

**11. Do you regularly (continuously) receive any medications not mentioned above?**

- ☐ No ☐ Yes (please list all medications that you remember of)

**12. Were you ever diagnosed with a cancer?** ☐ No ☐ Yes

If yes, did you receive oncological treatment during the last year? ☐ No ☐ Yes

**13. Do you have any known allergies?** ☐ No ☐ Yes

**QUESTIONS FOR WOMEN**

**14. Are you currently pregnant?** ☐ No ☐ Yes (how many weeks)

**15. Did you give birth during the last year?** ☐ No ☐ Yes (when) \_\_\_\_\_

Completion date \_\_\_\_ May/June (underline the applicable option) 2020
